 - Begin administration of study medication less than 2 hours prior to the skin incision on day of surgery in the preoperative area.
 - Record time of study medication administration
 - Record time of scheduled surgery (listed operating room time)
- AE assessment: including hypersensitivity reactions, which could include skin reactions, difficulty breathing, eye or nasal reactions, or gastrointestinal complaints, redness, tenderness, pain, or rash at the injection site or any clinically relevant abnormality (with exception of surgical scars) noted after the start of the study medication that was not present at screening.

8.3.2.2 Surgery:

The da Vinci[®] Fluorescence Imaging Vision System, SPY Elite Imaging System or Visionsense VSiii 3DHD system will be used to identify tumor lesions under normal/visible light and fluorescent light prior to surgical excision of lesions, and again after surgical excision of lesions to identify persistent lesions. The da Vinci system or Visionsense VSiii system will be used for all partial nephrectomies (robotic) and for robotic radical nephrectomies. The SPY Elite will be used for open radical nephrectomies. See **Appendix D** and **Appendix E** for more detailed information about the da Vinci and SPY camera/imaging systems. Information about the Visionsense VSiii system can be found at <http://www.visionsense.com/vsiii-system/>.

The Investigator will record the start and stop time for each exposure to fluorescence (pre-resection, post-initial resection, other [give reason]) in the eCRF. The total time of fluorescence will be calculated automatically.

Status	Time On Fluorescent Light	Time Off Fluorescent Light
Before surgical excision		
After initial surgical excision		
Other (explain reason)		

The number and location of suspect tumor lesions detected under **normal light and/or by palpation** will be recorded on the schematic (**Appendix B**) using an “O”. The number and location of suspect tumor lesions detected using **fluorescent light** will be recorded on the schematic using an “x” (for those lesions that were also identified under normal light and/or by palpation, the “x” will be superimposed on the “O” as “⊗”; and for those identified only under fluorescence, they will be recorded only by the “x”).

Light source	Notation
Visible light	O
Fluorescent	X
Both	⊗

For Partial Nephrectomies

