Surrounding perinephric fat will be removed as indicated for the renal mass. Then the renal mass will be visualized and photographed (video and still images) using visible light and fluorescent light. As described above, start and stop times of exposure to fluorescent light will be noted, and the number and location of fluorescent lesions related to the mass and surrounding renal parenchyma detected will be recorded on the schematic. Findings under visible light will also be recorded.

After the renal mass is removed, it will be processed by the operating surgeon and the frozen section pathology staff. The tumor margin will be inked and the tumor sectioned in 5mm thick cross-sectional slices. The tumor will then be returned to the operating room to be viewed and photographed with visible and fluorescent light. It will then be sent for pathologic processing as discussed in **Appendix B**.

For Radical Nephrectomies

The regional lymphadenectomy will be performed as per the standard of care for the patient’s renal mass. The renal mass will be visualized and photographed (video and still images) using visible and fluorescent light *through the surrounding perinephric fat*. The start and stop times of exposure to fluorescent light will be noted, and the number and location of fluorescent lesion/s related to the mass and surrounding renal parenchyma detected under fluorescent and visible light sources will be recorded on the schematic.

All identified nodal tissue from each marking (“O”, “X”, and “⊗”) will be excised, as determined by the Investigator, *under normal light*. Following the initial excision under normal light, the field will be illuminated with *fluorescent light* again to detect any remaining fluorescence-positive lesions. Any such lesions will be noted with a “P” on a schematic sheet (**Appendix C**) and excised as determined by the Investigator. A unique identifier will be assigned to each excised lesion, and the location for each lesion will be recorded on the schematic and in the eCRF. The reason for not excising any remaining lesion(s) will be noted. If no additional lesions are observed, this will be noted on the schematic and in the eCRF.

The nodal tissue will be processed by the operating surgeon and the frozen section pathology staff. The lymph nodal tissue will be marked with suture or clips to help with anatomic orientation of the specimen, and then sent for pathologic processing as discussed in the study pathology manual.

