12.7 Analysis of primary objective

The primary endpoint is to see if OTL38 and fluorescence imaging has sensitivity to detect RCC in the primary tumor (for partial nephrectomy) or in lymph nodes (for radical nephrectomy with lymph node dissection). Both sensitivity and the secondary endpoint of specificity will be assessed as follows: Final pathology and immunohistochemistry will serve as the gold standard with which gross observation and fluorescent imaging are compared for margin of resection, regional lymph nodes, and primary tumor. Pathology and immunohistochemistry results will be listed per patient. Times on and off for the imaging system will be listed per patient. Sensitivity, specificity, positive predictive value, and negative predictive value will be calculated for descriptive purposes although we understand the sample sizes are not large enough to estimate these values with a high level of accuracy at this stage. That would be accomplished in a future larger study. Sensitivity and specificity will be estimated using the method of Generalized Estimating Equations (GEE), which will take into consideration the correlated nature of multiple lesions removed from the same patient. Each patient will have all excised target lesions contributing to the data analysis (each type: O, x, ⊗, and P).

	Cancer +	Cancer-
Fluorescence+	True Positive (TP)	False Positive (FP)
Fluorescence-	False Negative (FN)	True Negative (TN)

Sensitivity (proportion of true positives) = $(TP/TP+FN) \times 100$

Specificity (proportion of true negatives) = $(TN/FP+TN) \times 100$

Sensitivity will be estimated using the GEE model for binomial distribution with fluorescence (-, +) as the fixed effect and patients as a random effect, and the 95% lower one-sided confidence interval for the true sensitivity will also be estimated. Specificity will be estimated using the GEE model for binomial distribution with fluorescence (-, +) as the fix effect and patients as a random effect, and the 95% lower one-sided confidence interval for the true specificity will also be estimated. Positive and negative predictive value will be estimated using similar methods.

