The deciding factors in choosing a camera system are related to safety, efficacy, and the manufacturer's ability to supply the appropriately tailored system. There are a number of variables, some biological, that affect efficacy. After an initial dose of intravenous OTL38, the compound will be widely dispersed in the body. Following a period of washout, only regions with a high folate receptor density are expected to retain the label. There is no predetermined critical saturation point that needs to be reached to make a tumor visible, and a lower concentration of labeling can be compensated for with a longer time of illumination and image capture. An excess of labeling can lead to decreased fluorescence through quenching, whereby neighboring emitted photons interfere with each other. This quenching would diminish over time as the concentration of label continued to decrease. The presence of labeling on a suspected tumor mass will not be the determining factor in whether the surgeon removes the mass or not in this study. The imaging is an adjunct to the surgeon's usual procedures of visualization, palpation, and experience.

A critical safety feature of the system is avoiding phototoxicity to the surgical area, surrounding tissues, or retinal tissues in patient or staff. Tissue damage can result either from exposure to high-intensity light or to heat generated by a light source. Injury to the surgical area is unlikely as the light is restricted by a barrier filter and thus contains only a fraction of the light energy released from the source. Both the light energy and the heat produced by this system are unlikely to cause tissue damage (**Appendix D & Appendix E**). A laser is present in the light source, and the IEC 60825-1:2007 standard for laser safety is applied to the light engine. This standard provides exposure limits that apply to any light source. For skin, in the wavelength region from 700-800 nm, the MPE (maximal permissible exposure) for skin tissue is set at 200 mW/cm². The duration for the exposure taken in the worst case situation is longer than 1000 seconds. The maximum heat produced by any component in the light path is less than 42 °C. Temperatures less than 42 °C are considered harmless by the European Medical Device Directive 93/42/EEC. The da Vinci[®] Fluorescence Imaging Vision System was built to avoid extraneous light release and thus prevent accidental exposure to light.

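### Section 12.7 analyses only excised lesions and has no rule for marked lesions left in place, so the Arm 2 accuracy figures are partly verified and could be biased in either direction

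*Combined protocol and SAP*

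**What the plan says.** Section 8.3.2.2 (Surgery, radical nephrectomies) marks suspect lesions O (normal light or palpation), X (fluorescence only) or ⊗ (both). Nodal tissue from each marking "will be excised, as determined by the Investigator". After that excision the field is lit again; any remaining fluorescent lesion "will be noted with a “P” on a schematic sheet" "and excised as determined by the Investigator". For lesions left behind, "The reason for not excising any remaining lesion(s) will be noted". Unique identifiers go to excised lesions.

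Section 12.7 takes final pathology and immunohistochemistry as the gold standard and states: "Each patient will have all excised target lesions contributing to the data analysis", listing types O, x, ⊗ and P. The opening of section 12 rules out imputation of missing data. Nothing in section 12 says what happens to a marked lesion that was not excised.

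Two other places describe the role of fluorescence in removal. Appendix D, section 19.4.1, says that labelling of a suspected tumour mass "will not be the determining factor in whether the surgeon removes the mass or not in this study" and calls imaging an adjunct to the surgeon's usual methods. Section 19.4.7 says that remaining fluorescent tissue is evaluated for tumour involvement and the operation finished as indicated.

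**The concern.** A lesion left in place has no pathology, so it has no cell in the 2×2 table of section 12.7. Verification is then partial, and whether a lesion is verified can depend both on the test result and on what the surgeon believes about the lesion. The protocol itself expects some benign signal: section 5.1.1 lists nonspecific localisation of OTL38, and section 19.4.1 describes autofluorescence and edge effects. A surgeon might well leave such spots alone.

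Sensitivity is at stake because section 12.3 makes an observed value below 70% in either arm a reason to refine the method before larger studies. Specificity is a stated secondary objective, and section 3.3 wants the pilot data to support larger protocols that estimate these accuracy measures. GEE handles correlation between lesions within a patient; it does not correct for lesions missing because of a clinical judgement.

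**Working it through.** **The plan's own figure.** The only computed design figure is the 88% chance of seeing a toxicity in section 12.3. It reproduces (1 − 0.9^20 = 0.878) but has no bearing here. The documents give no lesion counts, so every count below is assumed.

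**Formulas (section 12.7).** Sensitivity = TP/(TP+FN); specificity = TN/(TN+FP). PPV, for which the section writes out no formula, = TP/(TP+FP). X, ⊗ and P lesions are fluorescence-positive; O-only lesions are fluorescence-negative.

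**Illustration.** Assume 40 marked lesions in Arm 2: TP 14, FN 6, FP 8, TN 12. Drop the fluorescent lesions left in place, as section 12.7 would.

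| Fluorescent lesions left | Sensitivity | Specificity | PPV |
|---|---|---|---|
| None | 14/20 = 0.700 | 12/20 = 0.600 | 14/22 = 0.636 |
| 2 of 8 benign | 0.700 | 12/18 = 0.667 | 14/20 = 0.700 |
| 4 of 8 benign | 0.700 | 12/16 = 0.750 | 14/18 = 0.778 |
| 6 of 8 benign | 0.700 | 12/14 = 0.857 | 14/16 = 0.875 |
| Half of benign and half of cancers | 7/13 = 0.538 | 12/16 = 0.750 | 7/11 = 0.636 |
| Half of cancers only | 7/13 = 0.538 | 12/20 = 0.600 | 7/15 = 0.467 |

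Starting instead from FP 4 and TN 16, leaving 3 of the 4 false positives moves specificity from 16/20 = 0.800 to 16/17 = 0.941 and PPV from 14/18 = 0.778 to 14/15 = 0.933.

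- Specificity rises whenever false positives drop out and true negatives stay.
- PPV rises only if the lesions left are more often benign than those excised; it is unchanged if the mix is the same and falls if they are more often cancer.
- Sensitivity falls when fluorescent cancers are left. Here it crosses the 70% line.
- O lesions left in place act the other way: a missed O-only cancer removes a false negative and raises sensitivity, and a benign one removes a true negative and lowers specificity.

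**Another force.** Unmarked nodes from the standard lymphadenectomy are not among the listed lesion types. Adding an assumed 20 TN and 2 FN from them to the fully verified table gives specificity 32/40 = 0.800 and sensitivity 14/22 = 0.636. Their absence therefore pulls specificity down and sensitivity up.

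**Bounds.** Let a be the unexcised fluorescent lesions and b the unexcised O-only lesions, with TP, FN, FP and TN counted among excised lesions.

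- Sensitivity: TP/(TP+FN+b) to (TP+a)/(TP+a+FN)
- Specificity: TN/(TN+FP+a) to (TN+b)/(TN+b+FP)
- PPV: TP/(TP+FP+a) to (TP+a)/(TP+FP+a)

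For the row with 4 benign lesions left (TP 14, FN 6, FP 4, TN 12, a = 4, b = 0), the bounds are sensitivity 14/20 = 0.700 to 18/24 = 0.750, specificity 12/20 = 0.600 to 12/16 = 0.750, and PPV 14/22 = 0.636 to 18/22 = 0.818. The fully verified values (0.700, 0.600, 0.636) lie within them. The excised-only specificity of 0.750 sits at the top of its range.

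**The case against.** Four arguments tell against making more of this.

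- A reader might infer that section 8.3.2.2 orders removal of every fluorescence-only node while Appendix D forbids it. The documents do not support that. Both excision sentences in 8.3.2.2 carry the Investigator's discretion, that section expects some lesions to stay, and all three accounts leave the decision to the surgeon. Section 19.4.1 is also in the da Vinci appendix and speaks of a mass, although it does so for this study as a whole. What stands is a difference in wording: an excised X-only lesion has fluorescence as its only recorded finding, and no passage says how that fits with Appendix D.
- A reader might treat every P lesion as suspected on fluorescence alone. Re-imaging is meant to find persistent lesions, so a P mark can be residue at a site already marked ⊗.
- A reader might infer that specificity and PPV are inflated, perhaps greatly. With 15 true negatives and 10 benign fluorescence-only lesions, specificity is 15/25 = 60% if all ten are excised and 15/15 = 100% if none are. Those counts are assumed extremes, and the standard lymphadenectomy removes fluorescent nodes within its field anyway. Leaving out unmarked nodes also pushes specificity down.
- Section 12.7 calls the accuracy measures descriptive and concedes imprecision; section 12.8 compares numbers of lesions detected without limiting them to excised ones; and section 12 allows exploratory analyses. This lowers the consequence, but none of it discloses or bounds selective verification.

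**Conclusion.** The concern holds as a gap in the analysis rule. Arm 2 accuracy rests on a subset of marked lesions chosen partly by the surgeon's judgement, and section 12 neither counts nor bounds the rest. Under the assumed counts, excised-only specificity reads 0.667 to 0.857 against 0.600 when 25% to 75% of false positives are left, and sensitivity reads 0.538 against 0.700 when half the fluorescent cancers are left. These figures show what the rule permits; they do not predict what the trial will find. The net direction for specificity, PPV or sensitivity cannot be known from the documents, and the effect is nil if every marked lesion is excised. The three descriptions of how fluorescence bears on removal differ enough to need one statement, but they do not amount to a flat contradiction.

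**What to change.** 1. Reconcile sections 8.3.2.2, 19.4.1 and 19.4.7 in one statement of how far fluorescence alone may lead to removal. The choice is the sponsor's.
2. In section 12.7, keep every marked lesion (O, X, ⊗, P) in the dataset with its own identifier and an excised yes/no flag. An X lesion declined at first excision and later re-marked P is one lesion and should be counted once.
3. Tabulate unexcised lesions by marking and reason.
4. Report sensitivity, specificity and PPV for excised lesions as planned, and beside them the best-case and worst-case bounds that assign unexcised lesions, including unexcised O lesions, as cancer or benign.

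The cost is modest but real. Section 8.3.2.2 assigns identifiers only to excised lesions and asks for a reason only for those remaining after re-illumination, so the schematic and eCRF need a small addition. There is one extra descriptive table, and the reported figures will be wider or less favourable.

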Secondary Objectives:	
To assess the specificity of tumor fluorescence obtained using OTL38 with folate receptor alpha positive (FRα+) renal cell carcinoma cancer lesions detected via immunohistochemistry
 
To assess the agreement between fluorescence imaging using OTL38 and FRα by immunohistochemistry
 
To assess the agreement between fluorescence imaging using OTL38 and visual/tactile assessments
 
To assess inter-observer variation of tumor fluorescence images captured during surgery, physician rated usefulness of imaging, and safety of OTL38

Study Design:	
This is a pilot, phase 2, non-randomized study in patients with RCC, scheduled to undergo primary, partial, or radical nephrectomy. The current study will have 2 separate arms, but the data from each arm will not be compared with each other.
 
Arm 1: patients with partial nephrectomy for localized RCC
 
Arm 2: patients with radical nephrectomy and lymph node dissection for locally advanced or metastatic RCC

Test Drug/Dose:	OTL38 Injection: folate analog ligand conjugated with an indole cyanine-like green dye as a solution in vials containing 3 mL at 2 mg/mL provided by On Target, LLC. Single-dose 0.025 mg/kg administered IV, less than 2 hours prior to skin incision. Diphenhydramine 25 mg will be given prior to administering the study agent.
Duration of Treatment	
Patients will receive a single dose of OTL38 approximately 2 hours before skin incision.
 
Safety assessments will occur at follow-up phone visit at 10 days (± 3 days) and follow-up office visit at 1 month (± 14 days)

Camera Systems	
The da Vinci[®] Fluorescence Imaging Vision System manufactured by Intuitive Surgical, Inc. or the VSiii 3DHD system manufactured by Visionsense will be used in this study to visualize OTL38-labelled tumors during robotic partial and radical nephrectomies. The SPY Elite Imaging System manufactured by NOVADAQ will be used in open radical nephrectomies. These systems are not approved for use with OTL38, and are therefore considered investigational for purposes of this study.
 
The da Vinci[®] Fluorescence Imaging Vision System has integrated fluorescence imaging capable of providing real-time, imaging identification of fluorescently tagged objects.

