To further assess agreement of gross fluorescence with pathology, at least one representative lymph node biopsy done. Once the specimen is removed, it will be processed by the surgical team on the back table and sent to pathology for microscopic examination and immunohistochemistry assessment to determine if it contains FR α + cancer cells. The pathologist will be blinded to the fluorescence results of the tumor.

For All Surgeries

- Vital signs: recorded per institutional practice
- AE assessment: including hypersensitivity reactions, which could include skin reactions, difficulty breathing, eye or nasal reactions, or gastrointestinal complaints, redness, tenderness, pain, or rash at the injection site or any clinically relevant abnormality (with exception of surgical scars) that was not present at screening.
- Adverse device effects (ADE) assessment: the surgeon will examine the subject to confirm that there are no visible changes to skin (erythema or pigment darkening), tissue or organs related to fluorescence. Changes could be present but are likely due to the temperature of the cauterization as lesions are excised.
- Concomitant medications: record all intraoperative medications (this does not include normal saline or other routine maintenance intravenous fluids)

8.3.2.3 Post-surgery:

- Post-surgery questionnaire: the surgeon will complete a questionnaire describing the usefulness of the fluorescence imaging for tumor removal and to achieve a negative margin (**Appendix A**).
- Blinded surgeon assessment: A co-investigator, blinded surgeon who was not involved with the case will view the photographs and complete a questionnaire to assess inter-observer agreement (**Appendix A**).
- Type of RCC excision (radical, partial), need for blood transfusion and estimated blood loss
- Vital signs: recorded per institutional practice

- AE assessment: including hypersensitivity reactions, which could include skin reactions, difficulty breathing, eye or nasal reactions, or gastrointestinal complaints, redness, tenderness, pain, or rash at the injection site or any clinically relevant abnormality (with exception of surgical scars) that was not present at screening.
- ADE assessment: the surgeon will examine the subject to confirm that there are no visible changes to skin (erythema or pigment darkening), tissue or organs related to fluorescence.

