- Concomitant medications: record all postoperative medications (this does not include normal saline or other routine maintenance intravenous fluids)

8.3.3 In-hospital admission (Days 1-5):

- Blood samples: complete blood count w/ differential (CBC w/ diff) and basic metabolic panel (BMP) *on day 1 after surgery*
- Vital signs: recorded per institutional practice
- AE assessment: including hypersensitivity reactions, which could include skin reactions, difficulty breathing, eye or nasal reactions, or gastrointestinal complaints, redness, tenderness, pain, or rash at the injection site or any clinically relevant abnormality (with exception of surgical scars) that was not present at screening.
- ADE assessment: the surgeon will examine the subject to confirm that there are no visible changes to skin (erythema or pigment darkening), tissue or organs related to fluorescence.
- Concomitant medications: record all postoperative medications (this does not include normal saline or other routine maintenance intravenous fluids)

8.3.4 Hospital discharge (Day 2-6):

- Vital signs: recorded per institutional practice
- Review records relating to discharge: date and time that discharge order was written (must occur the same day)
- AE assessment: including hypersensitivity reactions, which could include skin reactions, difficulty breathing, eye or nasal reactions, or gastrointestinal complaints, redness, tenderness, pain, or rash at the injection site or any clinically relevant abnormality (with exception of surgical scars) that was not present at screening.
- ADE assessment: the surgeon will examine the subject to confirm that there are no visible changes to skin (erythema or pigment darkening), tissue or organs related to fluorescence.
- Concomitant medications: record all postoperative medications (this does not include normal saline or other routine maintenance intravenous fluids)

8.3.5 Follow-up phone call (Day 10 [±3 days]):

- AE assessment: including hypersensitivity reactions, which could include skin reactions, difficulty breathing, eye or nasal reactions, or gastrointestinal complaints, redness, tenderness, pain, or rash at the injection site or any clinically relevant abnormality (with exception of surgical scars) that was not present at screening.

- ADE assessment: the surgeon will examine the subject to confirm that there are no visible changes to skin (erythema or pigment darkening), tissue or organs related to fluorescence.

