- Concomitant medications: record any new medications taken since discharge
- A letter will be sent to any subject not contacted after 3 attempts by telephone

8.3.6 Follow-up appointment (1 Month [± 14 days]):

- Physical examination: including weight and vital signs (blood pressures, heart rate, respiratory rate, and temperature). The extent of the physical examination is determined by the investigator (or designee) and is based on clinical relevance to the subject's medical history and scheduled surgical procedure as per standard medical/surgical care.
- Blood samples: complete blood count with differential (CBC w/ diff) and complete metabolic panel (CMP)
- AE assessment: including hypersensitivity reactions, which could include skin reactions, difficulty breathing, eye or nasal reactions, or gastrointestinal complaints, redness, tenderness, pain, or rash at the injection site or any clinically relevant abnormality (with exception of surgical scars) that was not present at screening.
- ADE assessment: the surgeon will examine the subject to confirm that there are no visible changes to skin (erythema or pigment darkening), tissue or organs related to fluorescence.
- Concomitant medications: record any new medications since discharge or follow-up phone call

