16.2 Adverse Device Effects Definitions

16.2.1 Adverse Device Effect (ADE)

An ADE is defined as any untoward and unintended response to a medical device, in this study, the camera/imaging system. This definition includes any event resulting from insufficiencies or inadequacies in the instructions for use or the deployment of the device, as well as any event that is the result of a user error [ISO 14155-1:2003 (E) 3.1].

All ADEs noted during the study will be reported in the eCRF. Please refer to section 8.3.2.2 for a list of possible ADEs related to the camera/imaging system.

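### The intraoperative device-effect instruction suggests cautery as the cause before attribution, and the Day 10 telephone call requires an examination that cannot be done by telephone

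*Combined protocol and SAP*

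**What the plan says.** Section 8.3.2.2 (For All Surgeries) sets out the ADE check in these words: "the surgeon will examine the subject to confirm that there are no visible changes to skin". It goes on to cover tissue and organs, and limits the check to changes linked to fluorescence. The next sentence reads "Changes could be present but are likely due to the temperature of the cauterization as lesions are excised". Section 16.2.1 sends the reader back to the same place: "Please refer to section 8.3.2.2 for a list of possible ADEs related to the camera/imaging system".

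The examination sentence, without the cautery remark, is repeated at post-surgery, in hospital, at discharge, at Day 10 and at 1 month (sections 8.3.2.3 to 8.3.6). The Day 10 contact in section 8.3.5 is a telephone call, as its title, the synopsis and the study calendar all say, and its contact rule confirms it: "A letter will be sent to any subject not contacted after 3 attempts by telephone". Yet its bullet still begins "ADE assessment: the surgeon will examine the subject to confirm that there are no visible changes to skin (erythema or pigment darkening), tissue or organs". The calendar in section 8.2 marks an ADE assessment at that call, but a physical examination only at screening and at the 1-month appointment.

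Section 12.8 will summarise ADEs by body system, severity and causal relationship to the study device. The synopsis declares the camera systems investigational for use with OTL38.

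**The concern.** Two separate things are wrong with the instruction.

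First, it is leading. It asks the surgeon to confirm an absence and names a non-device cause for anything found. Section 5.1.1 lists phototoxicity or thermal damage from the light source among the risks, and Appendix D (19.4.1) says tissue damage can come from intense light or from a light source's heat. Cautery is therefore a competing explanation for the very effect under surveillance, and the protocol gives no criterion to tell the two apart. At stake is the column of the ADE table that states relationship to the device.

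Second, the Day 10 examination cannot be done. Sites must either leave it blank, improvise, or enter a negative finding with no examination behind it. Nothing in section 8.3.5 says which, so Day 10 ADE entries may not mean the same thing from one patient to the next.

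**Working it through.** This is mainly a comparison of passages; the arithmetic is small.

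**1. From a visible change to the ADE table.**
- Section 16.2.1 defines an ADE as an untoward, unintended response to the device. The definition is causal, so a change ascribed to cautery at the operating table need not be entered as an ADE at all.
- Section 12.8 tabulates ADEs by relationship to device. A change never entered as an ADE cannot appear there, even as unlikely related.
- The only graded attribution scale, section 16.1.4, is headed for the investigational agent(s). Its rows speak of the agent or intervention and do not separate camera, drug and surgery.

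**2. What is captured whatever the cause.**
- Appendix A asks the primary surgeon, straight after the case, whether there are visible organ or skin changes, with yes/explain or no as answers (partial nephrectomy items 11 and 12; radical nephrectomy items 8 and 9). These items mention neither cautery nor fluorescence as a cause.
- Section 9 has clinically relevant new abnormalities, surgical scars excepted, recorded as AEs. Section 16.3 records AEs for at least 30 days regardless of relatedness.
- However, no text carries the Appendix A answers into the ADE record. Section 12.8 mentions the surgeons' questionnaire only under usefulness.

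The record of the change is therefore largely protected. Its attribution to the device is not.

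**3. Contacts with an ADE assessment (section 8.2 calendar).**

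| Contact | Skin can be examined | Internal tissue or organs can be seen |
|---|---|---|
| Surgery | yes | yes |
| Post-surgery | yes | not after closure |
| In hospital | yes | no |
| Discharge | yes | no |
| Day 10 telephone call | no | no |
| 1-month appointment | yes | no |

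One of six contacts cannot be executed at all: 1/6 = 17%. With 20 patients all completing follow-up, that is 20 × 1 = 20 of 20 × 6 = 120 scheduled assessments. The tissue-or-organs element also fails at the in-hospital, discharge and 1-month visits, which with Day 10 makes four of six, and at post-surgery too if that check follows closure.

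**4. The plan's only safety probability.** Section 12.3 gives 88% for seeing at least one toxicity in 20 patients at a true rate of 0.10. Check: 1 − 0.90^20 = 0.878, so it reproduces. It assumes that every event is recognised.

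The documents give no rate at which device effects would be attributed to the device. Purely as an illustration, assume a true device-effect rate of 0.10 and let s be the share attributed to the device. The chance that at least one is listed as device-related is 1 − (1 − 0.10s)^20:

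| s (assumed) | Probability |
|---|---|
| 1.00 | 0.878 |
| 0.90 | 0.848 |
| 0.75 | 0.790 |
| 0.50 | 0.642 |
| 0.25 | 0.397 |

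This shows direction only. Section 12.3 speaks of toxicity in general, and no value of s can be defended from the documents.

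**The case against.** The strongest reply is that neutral recording already exists. Appendix A collects visible changes on the day of surgery without a suggested cause, and Section 9 and section 16.3 collect AEs whatever their cause. The cautery sentence appears once, states an expectation and gives no coding rule. It has some basis: section 5.1.1.1 places the imaging system within safety limits, and Appendix D puts the maximum heat of any component in the da Vinci light path below 42 °C. The reference in section 16.2.1 is to types of effect, not to a rule of attribution. At Day 10, the AE bullet for the same call already covers skin reactions, which a patient can report, and the ADE bullet looks copied from the in-person visits. Safety is a descriptive secondary endpoint in a 20-patient pilot, and no numerical stopping rule uses ADE counts.

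Most of this stands, and it limits the point. A reader might infer that device effects will go unrecorded, or that the whole ADE assessment is tilted towards none. The documents do not support that: the safeguards capture the changes, and the cautery sentence is absent from the five later assessments. A reader might also infer that Day 10 yields no usable safety information; the AE questions in the same call say otherwise.

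Three things survive. A low expected risk is no reason to tell the assessor the likely cause in advance, since that is what the assessment is meant to find out. The safeguards do not repair attribution, because nothing routes Appendix A into the ADE table. And the Day 10 bullet, whatever its origin, conflicts with the format of the contact.

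**Conclusion.** The point holds in a limited form. The intraoperative instruction can push attribution in the section 12.8 ADE table away from the device, although the changes themselves are recorded elsewhere. The size of this effect, and whether it would occur at all, cannot be computed from the documents; the direction is a judgement from the wording. The second part needs no assumption: one of six ADE contacts, in every patient, cannot be carried out as written, and the tissue-or-organs wording cannot be met at in-person visits after closure. The consequence is confined to the device-safety description. The efficacy endpoints are not touched. Since the cameras are investigational here and the correction is cheap, the wording should be changed.

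**What to change.** 1. Delete the cautery sentence from section 8.3.2.2.
2. Carry any yes on Appendix A items 11 and 12 (partial nephrectomy) or 8 and 9 (radical nephrectomy) into the ADE form. Rate causality for the camera separately from OTL38 and from surgery or cautery, using the section 16.1.4 categories, and say in section 12.8 that these entries feed the ADE table.
3. Reconcile section 8.3.5 with the telephone format: ask scripted questions about skin changes and record the answers as 'reported, not examined'.
4. In the ADE bullets for contacts after closure, limit the examination to what can be seen, namely skin and wound.

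The cost is protocol and case report form wording, with no added visit or procedure. The downside is that a few more events may be listed as possibly device-related, some of them probably due to cautery; the separate surgery rating will show that.
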